6.3.1 Facility characteristics

Each facility will be descriptively summarized using data from separately completed facility level questionnaires; these questionnaires will be administered twice - at the start and end of the HCW level survey at each facility. This data will then be linked to HCW level data from the same facility to provide a broader context for the survey data, as well as to compare the results from HCW level survey with what could have been expected from the facility level data. Subsequently, an assessment of potential biases and limitations in this regard will be discussed in a study report.

In particular, a description of facilities will be provided in terms of type (public/private/community; teaching status) and size (number of beds), as well as existence of policies for prophylactic treatment and PPE use to prevent COVID-19 among HCWs. In addition, existence of BCG vaccination policy for HCWs and shortage of COVID-19 tests experienced by the facility will be described, as recorded in the facility level survey.

Also, the number of HCWs exposed to COVID-19 patients at each facility, the number of HCWs tested for, diagnosed with and died due to COVID-19 at each facility will be described, both since the start of pandemic (including within the last 30 days) and at the end of the survey in the facility.

The number of patients tested and treated for COVID-19 at each facility will be described too.

6.3.2 Demographic characteristics

The following demographic characteristics of subjects included in the study will be descriptively summarized for HCWs with and without COVID-19 infection (see Table 8.2.3 in the appendix):

- Age (Years)
- Biological Gender (Male; Female)
- Race (White; Black; Mixed race; Asian Indian; Asian Bangladeshi; Asian Pakistani; Other Asian; Other)

- Blood Type (A positive; A negative; B positive; B negative; O positive; O negative; AB positive; AB negative; Unknown)
- BMI in kg/m²(derived from height (cm) and weight (kg) and grouped into the following categories: Normal weight (BMI of 18.5 to less than 25); Overweight (BMI of 25 to less than 30); Obese (BMI of 30 or greater); Underweight (BMI of less than 18.5); Missing)
- Smoking Status (Current Smoker; Past Smoker; Never Smoked)

6.3.3 Household characteristics

The following household characteristics of subjects included in the study will be descriptively summarized for HCWs with and without COVID-19 infection (see Table 8.2.4 in the appendix):

- Others in household exposed to COVID-19 infected individuals (Yes; No; Unknown)
- Number of household members exposed to COVID-19 infected individuals
- Others in household showing symptoms of COVID-19 (Yes; No)
- Number of household members showing symptoms of COVID-19
- Others in household diagnosed with COVID-19 (Yes; No)
- Number of household members diagnosed with COVID-19
- Number of people living in household

For HCWs with COVID-19 at entry: responses to the baseline survey will be used.

For HCWs with COVID-19 at follow-up: maximum responses over the entire follow-up time available in the data cut. In addition, maximum responses in the 2 or 4 weeks (TBD) prior to COVID-19 infection date will be described.

For HCWs with no COVID-19 infection at any time: maximum responses over the entire follow-up time available in the data cut. In addition, maximum responses in the 2 or 4 weeks (TBD) prior to the data cut date will be described.

Maximum responses will be defined as:

- For a yes/no question, “yes” will be considered
- For number of household members, the maximum number will be considered

6.3.4 Exposure to COVID-19 patients

The following household characteristics of subjects included in the study will be descriptively summarized for HCWs with and without COVID-19 infection (see Table 8.2.5 in the appendix):

- Contact with confirmed COVID-19 patients (Yes; No)
- Direct care to COVID-19 patients (Yes; No)
- Face-to-face contact (within 1 metre) of COVID-19 patients (Yes; No)

- Present when aerosol generating procedures performed (Yes; No)
- Average number of COVID-19 patients in contact each week for past month
- Number of days spent at work in last week
- Number of hours worked directly with COVID-19 patients in last week

For HCWs with COVID-19 at entry: responses to the baseline survey will be used.

For HCWs with COVID-19 at follow-up: maximum responses over the entire follow-up time available in the data cut. In addition, maximum responses in the 2 or 4 weeks (TBD) prior to COVID-19 infection date will be described.

For HCWs with no COVID-19 infection at any time: maximum responses over the entire follow-up time available in the data cut. In addition, maximum responses in the 2 or 4 weeks (TBD) prior to the data cut date will be described.

Maximum responses will be defined as:

- For a yes/no question, “yes” will be considered
- For number of days spent at work and number of hours worked directly with the COVID-19 patients, a summation will be done
- For average number of COVID-19 patients in contact each week for past month, an average will be calculated

Using the follow-up survey data for questions with yes/no responses, the following plot will be generated to display exposure over time:

For,

i = question #

n_{it} = # of yes answers to question i at time t

n_t = # of responders at time t

$$r_t = \sum_i n_{it}/n_t$$

A line plot of r over time will then be displayed. Two separate lines will be generated, one for HCWs infected with COVID-19 and another for HCWs that were never infected with COVID-19.

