Pneumonia	X	X	-
Nausea or vomiting	X	X	-
Headache or migraine	X	X	-
Abdominal pain (pain in tummy)	X	X	-
Asthenia (weakness or loss of strength)	X	X	-
Arthralgia (joint pain)	X	X	-
Anosmia (loss of smell)	X	X	-
Ageusia (loss of taste)	X	X	-
Blue coloring in toes	X	X	-
Diarrhea (two or more looser-than-normal stools in 24 hours)	X	X	-
SARS-CoV-2 testing			
Tested? (yes/no)	X	X	-
Type of test	X	X	-
PCR (positive/negative)	X	X	-
Antigen test (positive/negative)	X	X	-
Serology (IgG and/ or IgM, positive/negative or titer)	X	X	-
Date of test	X	X	-
Serology testing	X	X	-
Household history (COVID-19)			
Number of household contacts	X	X	-
Additional household member(s) exposed to COVID-19 (yes/no) If yes, how many?	X	X	-
Additional household member(s) with symptoms consistent with COVID-19 (yes/no) If yes, how many?	X	X	-
Additional household member(s) diagnosed with COVID-19 (yes/no) If yes, how many?	X	X	-
Underlying conditions and key morbidities			
Chronic lung disease	X	-	-
Diabetes mellitus	X	-	-
Cardiovascular (heart) disease	X	-	-
Chronic renal (kidney) disease	X	-	-
Chronic liver disease	X	-	-
Immunocompromised condition (HIV/AIDS, organ transplant, other)	X	-	-
Tuberculosis	X	-	-
Neurologic/neurodevelopmental	X	-	-
Hypertension (high blood pressure)	X	-	-
History of stroke	X	-	-
Other chronic diseases	X	-	-
If female, currently pregnant	X	-	-
If female, currently breastfeeding/lactating	X	-	-
Job characteristics			
Type of healthcare work	X	-	-

Primary work location (ED, ICU, Medical floor)	X	X	-
Number of hours with patients	X	X	-
Concomitant medications (other than for COVID-19)			
Antibiotics (yes/no)	X	X	-
Antimalarials (yes/no)	X	X	-
Antiparasitics (yes/no)	X	X	-
Antiretrovirals for HIV (yes/no)	X	X	-
Antivirals (yes/no)	X	X	-
Medication for high blood pressure and cardiovascular disease (yes/no)	X	X	-
Nonsteroidal Anti-inflammatory Drugs (NSAIDs) (yes/no)	X	X	-
Botanicals (yes/no)	X	X	-
Immunocompromising drugs (yes/no)	X	X	-
COVID-19 vaccine (to be selected as applicable)			
Convidicea (Ad5-nCoV)	X	X	
CoronaVac (Sinovac)	X	X	
Covaxin (BBV152)	X	X	
EpiVacCorona (Vector Institute)	X	X	
Janssen Pharmaceuticals (Johnson & Johnson) (Ad26.COV2.S)	X	X	
Moderna COVID-19 Vaccine	X	X	
Novavax (NVX-CoV2373)	X	X	
Oxford-AstraZeneca COVID-19 Vaccine	X	X	
Pfizer-BioNTech COVID-19 Vaccine	X	X	
Sinopharm BBIBP-CorV	X	X	
Sputnik V COVID-19 Vaccine	X	X	
Other (please specify)	X	X	

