3.6 Other study variables

All of the following variables are collected at baseline and for each week of follow-up up to 12 weeks.

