3.6.3 History of exposure to COVID-19 patients

- At enrollment
 - Self-reported ongoing and recurrent exposure (yes/no)
 - WHO exposure definition (3 questions) (yes/no)
 - Direct patient care (yes/no)
 - Face-to-face contact (yes/no)
 - Present during aerosol-generating procedure (yes/no)

- Weekly follow-up
 - Self-reported ongoing and recurrent exposure (yes/no)
 - WHO exposure definition (3 questions) for past week
 - Days worked past week
 - Number of COVID-19 cases exposed to in the past week

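### Descriptive tables in SAP 6.3 put groups on unequal time scales: weekly days and hours are summed beside a single baseline survey, and the uninfected window is tied to the data cut

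*SAP*

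**What the plan says.** SAP 6.3.4 describes exposure to COVID-19 patients in three groups: healthcare workers (HCWs) with COVID-19 at entry (entry cases), those infected during follow-up (follow-up cases), and those never infected.

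- **Entry cases:** "For HCWs with COVID-19 at entry: responses to the baseline survey will be used".
- **The other two groups:** a maximum response over all follow-up in the data cut. For two items the maximum is defined as a total: "For number of days spent at work and number of hours worked directly with the COVID-19 patients, a summation will be done". For patient contacts it is a mean: "For average number of COVID-19 patients in contact each week for past month, an average will be calculated".
- **Labels:** both summed items ask about the last week. Table 8.2.5 keeps those row labels, sets the groups in adjacent columns and is titled as a baseline table. Tables 8.2.4, 8.2.7 and 8.2.9 are also titled as baseline, although the text behind them (6.3.3, 6.3.6, 6.3.8) uses windows that run through follow-up.
- **Additional window:** for follow-up cases, "maximum responses in the 2 or 4 weeks (TBD) prior to COVID-19 infection date will be described"; for the never infected, "maximum responses in the 2 or 4 weeks (TBD) prior to the data cut date will be described". Sections 6.3.3, 6.3.6, 6.3.7 and 6.3.8 use the same two anchors.
- **Follow-up:** weekly surveys for 12 weeks from each HCW's own enrolment (SAP 3.1 and 3.4). Protocol 9.5 ends the study 12 weeks after the last participant enters.
- **Collection schedule:** SAP 3.6 says "All of the following variables are collected at baseline and for each week of follow-up up to 12 weeks". SAP 3.6.3 and protocol Appendix 2 list "Days worked past week" at weekly follow-up only. Appendix 2 schedules "Number of hours with patients" at enrolment and weekly.
- **Recall:** footnote c to protocol Table 1 extends the weekly follow-up column to the time since the last follow-up when that is longer.

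**The concern.** A reader of Table 8.2.5 will assume that its columns measure the same thing. In the days and hours rows they do not: one column holds a one-week answer and the others hold a total of up to 12 such answers.

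The additional window has a different fault. It is the SAP's own way of looking at follow-up cases before infection, so it is the natural place to compare infected with uninfected HCWs. Cases are placed at their own infection date. Uninfected HCWs are placed at a calendar date that may lie after their follow-up has ended. Nothing in the SAP ties that window to the HCW's own last survey.

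At stake is the descriptive comparison for household, patient-contact, medication, prophylaxis and PPE items. Several of these are factors named in the secondary objectives (SAP 2.2). The note under SAP Table 5.4.1 also leaves composite variables and collapsed categories to be decided after the descriptive analyses, so a misread table could influence those choices indirectly.

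**Working it through.** The point rests on stated rules, so there is no figure in the plan to reproduce. The checks show what the rules produce.

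**1. Sum against a single survey.** Assume a constant week of 5 days and 20 hours. A sum over n one-week answers is n times the weekly value.

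| Surveys | Days | Hours |
|---|---|---|
| 1 (entry case, baseline) | 5 | 20 |
| 12 (full follow-up) | 5 × 12 = 60 | 20 × 12 = 240 |

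The ratio for hours is 240 / 20 = 12, with no difference in workload. This needs the enrolment and weekly hours items to ask the same question, and the survey wording is not in the documents. For days, the entry-case cell may be empty, because two of the three places that list the item schedule it at follow-up only.

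**2. Missed surveys.** Suppose 6 of 12 surveys are answered, at 5 days per week.

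| Recall | Sum | Per completed survey | Per week covered |
|---|---|---|---|
| One week (item labels) | 5 × 6 = 30 | 30 / 6 = 5 | 30 / 6 = 5 |
| Since last follow-up (footnote c), 6 surveys covering 12 weeks | 5 × 12 = 60 | 60 / 6 = 10 | 60 / 12 = 5 |

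The sum falls with missed surveys only under one-week recall. A mean per completed survey is wrong under the footnote. Only the value per week covered is right under both.

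**3. Uninfected HCWs with any survey in the data-cut window.** The documents give neither the enrolment length nor the cut date. Assume uniform enrolment over W weeks, full follow-up and a final cut at week W + 12. An HCW enrolled at week e has a last survey at e + 12. It falls in the last k weeks if e > W − k, so the share is k / W.

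| W (weeks) | k = 4 | k = 2 |
|---|---|---|
| 8 | 50.0% | 25.0% |
| 12 | 33.3% | 16.7% |
| 26 | 15.4% | 7.7% |
| 52 | 7.7% | 3.8% |

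With a cut 4 weeks later still, the share is 0%. With an interim cut on the last enrolment day, counting the enrolment survey, the share is min(1, (12 + k) / W). That is 100% for W = 12; 61.5% (k = 4) and 53.8% (k = 2) for W = 26; 30.8% and 26.9% for W = 52.

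**4. Study time of the surveys compared.** At the final cut, the uninfected surveys inside the window have mean study week 11.0 (k = 4) or 11.7 (k = 2). If infection is first reported evenly over surveys 1 to 12 (assumed), cases' pre-infection surveys have mean study week 202 / 38 = 5.3 (k = 4) or 121 / 21 = 5.8 (k = 2).

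**5. Post-infection weeks in the cases' main window.** On the same assumption, the mean of 12 − j over j = 1 to 12 is 5.5 surveys, and 5.5 / 12 = 46%.

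**The case against.** **Cumulative exposure is a legitimate summary.** Follow-up cases and uninfected HCWs share the main window and the same sum, and the rule for entry cases is openly stated. This stands for those two columns, as long as the weeks covered are equal. It does not rescue the entry-case column: a single baseline survey cannot be cumulative, and the row labels still say one week. If the table is truly baseline for every column, the title and the text of 6.3.4 contradict each other.

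**Other planned outputs compare the groups over time.** Section 6.3.4 plans a line plot of yes answers divided by responders at each time, by infection status. Sections 6.3.7 and 6.3.8 plan stacked bars by survey date. These partly cover the yes/no exposure, prophylaxis and PPE items. They do not cover the household, medication or count rows.

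**Prophylaxis has start and stop dates.** Use in a window can be derived without a survey falling in it, so the shares in step 3 do not carry over to 6.3.7. A window after the HCW's own follow-up is still unobserved there.

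A reader might also infer more than the documents support:

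- *The sum always falls with missed surveys.* Footnote c to protocol Table 1 leaves this open.
- *Most uninfected HCWs will be lost from the additional window.* That depends on two dates that are not given. An early interim cut may lose none.
- *The primary hazard ratio is biased by these rules.* Days and hours are not in SAP Table 5.4.1, and the window rules appear only in 6.3.

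**Conclusion.** The point holds as a minor one, confined to descriptive tables; the primary Cox model is not directly affected.

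- **Scale.** Days and hours in Table 8.2.5 are not comparable between entry cases and the other columns. The gap reaches 12-fold for equal weekly hours, on the assumption that the enrolment and weekly items match.
- **Window.** In five sections, uninfected HCWs whose 12 weeks ended before the window contribute no survey to it. At a final cut with 26-week uniform enrolment and full follow-up (assumed), 15% or 8% have any survey in the 4- or 2-week window. The actual share cannot be known from the documents.
- **Labelling.** Four table titles say baseline over windows that run through follow-up. The cases' main window includes post-infection weeks without saying so.

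The missed-survey effect and the entry-case cell for days are inconsistencies to reconcile, not established errors in a particular direction.

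**What to change.** 1. **SAP 6.3.4:** report days and hours per week covered, that is, the sum divided by the weeks the answered surveys cover. This equals the number of completed surveys only if recall is one week. Reconcile the one-week item labels with footnote c to protocol Table 1 first.
2. **Tables 8.2.4, 8.2.5, 8.2.7 and 8.2.9:** replace the baseline wording in the titles with the window that applies to each column.
3. **Days worked:** reconcile SAP 3.6 with SAP 3.6.3 and protocol Appendix 2 on whether the item is collected at enrolment, then fill or drop the entry-case cell.
4. **SAP 6.3.3, 6.3.4, 6.3.6, 6.3.7 and 6.3.8:** end the uninfected window at each HCW's own last completed survey or end of follow-up. Every uninfected HCW with a follow-up survey then contributes. Footnote that this window falls later in study time than the cases' window: surveys 9 to 12, mean week 10.5, against 5.3 for the 4-week window under the assumptions above.
5. **Main window for follow-up cases:** footnote that it includes post-infection weeks. Use the equal-length pre-infection and own-follow-up windows for the infected-versus-uninfected comparison.

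The cost is SAP wording, titles, footnotes and minor table reprogramming, with no new data. Matching the uninfected window to cases on study week and calendar date would remove the timing difference, but it needs matching rules across five sections and is an optional refinement.

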6.3.5 Medical history

The following medical conditions of subjects included in the study will be descriptively summarized for HCWs with and without COVID-19 infection (see Table 8.2.6 in the appendix):

- Any of the following conditions (Chronic lung disease; Diabetes; Cardiovascular (heart) disease); Chronic renal (kidney) disease; Chronic liver disease; Immunocompromised condition; Cancer, Obesity; Tuberculosis; Neurologic/neurodevelopmental; History of stroke; Hypertension (high blood pressure); Other chronic diseases; None of the above)

To note, for HCWs who entered the survey with already confirmed or symptomatic COVID-19 disease (whether at entry or prior to entry), it will not be possible to attribute conditions listed under medical history section to the timeframe prior to or following COVID-19 disease, as these conditions are collected at entry with no recorded date of diagnosis. This is unlikely to be an issue for the chronic conditions listed, however this could pose a problem for including cardiovascular disease and history of stroke in the causal inference models outlined in the primary analysis. This issue will be assessed during the subgroup analysis of HCWs by COVID-19 status at study entry.

6.3.6 Medications for non-COVID-19 related purposes

The following medications for non-COVID related purposes will be descriptively summarized for HCWs with and without COVID-19 infection (see Table 8.2.7 in the appendix):

- Antibiotics (yes/no). If yes, please specify.
 - Azithromycin
 - Trimethoprim/sulphamethoxazole
 - Macrolide antibiotics (roxithromycin, clarithromycin, erythromycin)
 - Other antibiotics
- Antimalarials (yes/no). If yes, please specify.
 - Hydroxychloroquine
 - Chloroquine
 - Sulfadoxine-pyrimethamine (SP)
 - Other antimalarials
- Antiparasitics (yes/no). If yes, please specify.
 - Ivermectin(yes/no)
 - Other antiparasitics
- Antiretrovirals for Human Immunodeficiency Virus (HIV) (yes/no). If yes, please specify.
 - Lopinavir
 - Ritonavir
 - Tenofovir
 - Nelfinavir
 - Other antiretrovirals
- Antivirals (yes/no). If yes, please specify.

- Oseltamivir
 - Favipiravir
 - Arbidol
 - Anti-hepatitis C treatments
 - Remdesivir
 - Other antivirals
- Medication for high blood pressure and cardiovascular disease (yes/no). If yes, please specify.
 - Angiotensin-converting enzyme (ACE) inhibitor (e.g. lisinopril, enalapril)
 - Angiotensin II receptor blockers (ARB) inhibitor (e.g. losartan, irbesartan)
 - Other anti-hypertensive for high blood pressure
 - Other medicine for high blood pressure and cardiovascular disease (E.g. antiarrhythmics, inotropes, chronotropes)
- Nonsteroidal Anti-inflammatory Drugs (NSAIDs) E.g. Aspirin, Ibuprofen, Indomethacin, Celecoxib, Diclofenac(yes/no). If yes, please specify.
- Botanicals (yes/no)
 - Artemisia teas (COVID Organics)
- Immunocompromising drugs (yes/no). If yes, please specify.
 - Corticosteroids
 - Cancer chemotherapy
 - Cyclosporine
 - Drugs for autoimmune conditions such as lupus or rheumatoid arthritis, Crohn's disease

For HCWs with COVID-19 at entry: responses to the baseline survey will be used.

For HCWs with COVID-19 at follow-up: medications used at any time over the entire follow-up time available in the data cut. In addition, medications used at any time in the 2 or 4 weeks (TBD) prior to COVID-19 infection date will be described.

For HCWs with no COVID-19 infection at any time: medications used at any time over the entire follow-up time available in the data cut. In addition, medications used at any time in the 2 or 4 weeks (TBD) prior to the data cut date will be described.

6.3.7 Prophylactic medications

Prophylaxis usage of subjects included in the study will be descriptively summarized for HCWs with and without COVID-19 infection (see Table 8.2.8 in the appendix):

A stacked bar chart will be used to display the prophylaxis usage during the follow-up period. The x-axis will be dates of survey responses and the stacked bars will be grouped by yes/no (corresponding to prophylaxis use at specific dates). This will be done separately for HCWs infected with COVID-19 and those uninfected. The stacked bar charts can be used to compare prophylaxis use among infected/uninfected HCWs over time. This will be done for “any prophylaxis use” and if sample if sample sizes permit they will

be presented for the major individual prophylaxis treatments (ie. azithromycin, chloroquine/hydroxychloroquine, ivermectin, lopanavir).

Prophylaxis usage pre- and post- first date of COVID-19 exposure will also be described, stratified further by COVID-19 infection status.

- Types, intake frequency, and doses of prophylactic treatments
 - Treatment name
 - Date started
 - Date stopped
 - Dose (intake)
 - Duration of treatment
 - Dose frequency and dosing interval
 - Status (stopped/ongoing)
 - Reason for stopping (not available/side effects/expense/other)
 - Number of missed doses and reason (not available/side effects/expense/other)

For HCWs with COVID-19 at entry: prophylaxis treatments used before the COVID-19 infection date will be described.

For HCWs with COVID-19 at follow-up: prophylaxis treatments used over the entire follow-up time available in the data cut. In addition, prophylaxis treatments used within 2 or 4 weeks (TBD) before COVID-19 infection date will be described.

For HCWs with no COVID-19 infection at any time: prophylaxis treatments used over the entire follow-up time available in the data cut. In addition, prophylaxis treatments used within 2 or 4 weeks (TBD) prior to the data cut date will be described.

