6.3.8 PPE usage

The following PPE usage of subjects included in the study will be descriptively summarized for HCWs with and without COVID-19 infection (see Table 8.2.9 in the appendix):

A stacked bar chart will be used to display PPE usage during the follow-up period. The x-axis will be dates of survey responses and the stacked bars will be grouped by yes/no (corresponding to PPE use at specific dates). This will be done separately for HCWs infected with COVID-19 and those uninfected. The stacked bar charts can be used to compare PPE use among infected/uninfected HCWs over time. This will be done for the four types of PPE (eg. masks, eye protection, gowns, gloves).

- PPE used in workplace since first known contact with COVID-19 patients
 - Mask (Yes always; Yes not always; No)
 - Type of Mask (N95 Respirator Mask; Other)
 - Eye Protection (Yes always; Yes not always; No)

- Gown (Yes always; Yes not always; No)
- Gloves (Yes always; Yes not always; No)
- The number of PPEs used as “yes always” among mask, eye protection, gown, gloves will also be summarized: none, one, two, three, all four

For HCWs with COVID-19 at entry: responses to the baseline survey will be used

For HCWs with COVID-19 at follow-up: overall PPE usage over the entire follow-up time available in the data cut. In addition, overall PPE usage in the 2 or 4 weeks (TBD) prior to COVID-19 infection date will be described.

For HCWs with no COVID-19 infection at any time: overall PPE usage over the entire follow-up time available in the data cut. In addition, overall PPE usage in the 2 or 4 weeks (TBD) prior to the data cut date will be described.

Overall PPE usage will be defined as the following from multiple weekly surveys being considered as above:

Responses seen in all weekly surveys being considered	Overall PPE usage
Yes always	Yes always
Yes always Yes not always	Yes not always
Yes always No	Yes not always
Yes always Yes not always No	Yes not always
Yes not always	Yes not always
Yes not always No	Yes not always
No	No

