9.1 Shell tables

Table 8.2.1 COVID-19 exposure status among all screened healthcare workers

Characteristic	Infected at baseline N = xxx	Infected during follow-up N = xxx	Uninfected N = xxx	Total
Exposed to COVID-19 infected patients prior to enrollment	xx (xx.x)	xx (xx.x)	xx (xx.x)	xx (xx.x)
Exposed to COVID-19 infected patients within 30 days of enrollment	xx (xx.x)	xx (xx.x)	xx (xx.x)	xx (xx.x)

Table 8.2.2 Primary and Secondary Outcomes at baseline and follow-up among the overall population

Outcomes	Total N=	Prophylaxis exposure		PPE usage	
		Yes N=	No N=	Yes N=	No N=
Primary Outcome					
SARS-CoV-2 infection among HCWs exposed to COVID-19 patients	xx (xx.x)	xx (xx.x)	xx (xx.x)	xx (xx.x)	xx (xx.x)
Secondary Outcomes					
SARS-CoV-2 uninfected HCWs	xx (xx.x)	xx (xx.x)	xx (xx.x)	xx (xx.x)	xx (xx.x)
SARS-CoV-2 infection with ambulatory status and no limitation of activities	xx (xx.x)	xx (xx.x)	xx (xx.x)	xx (xx.x)	xx (xx.x)
SARS-CoV-2 infection with ambulatory status and limitation of activities	xx (xx.x)	xx (xx.x)	xx (xx.x)	xx (xx.x)	xx (xx.x)
Hospitalized due to COVID-19 illness with mild disease	xx (xx.x)	xx (xx.x)	xx (xx.x)	xx (xx.x)	xx (xx.x)
Hospitalized due to COVID-19 illness with severe disease	xx (xx.x)	xx (xx.x)	xx (xx.x)	xx (xx.x)	xx (xx.x)
All-cause mortality	xx (xx.x)	xx (xx.x)	xx (xx.x)	xx (xx.x)	xx (xx.x)

Table 8.2.3 Static Variables by COVID-19 indication

Characteristic	Parameter	Infected	Uninfected	Total
		N=	N=	N=
Age (years)	N	xx	xx	xx
	Mean (SD)	xx.x (xx.x)	xx.x (xx.x)	xx.x (xx.x)
	Median	xx	xx	xx
	Min-Max	xx-xx	xx-xx	xx-xx
	IQR	xx	xx	xx
Biological Gender	Female	xx (xx.x)	xx (xx.x)	xx (xx.x)
	Male	xx (xx.x)	xx (xx.x)	xx (xx.x)
BMI	Normal Weight	xx.x (xx.x)	xx.x (xx.x)	xx.x (xx.x)
	Overweight	xx.x (xx.x)	xx.x (xx.x)	xx.x (xx.x)
	Obese	xx.x (xx.x)	xx.x (xx.x)	xx.x (xx.x)
	Underweight	xx.x (xx.x)	xx.x (xx.x)	xx.x (xx.x)
	Unknown	xx.x (xx.x)	xx.x (xx.x)	xx.x (xx.x)
Smoking status	Current Smoker	xx (xx.x)	xx (xx.x)	xx (xx.x)
	Past Smoker	xx (xx.x)	xx (xx.x)	xx (xx.x)
	Never Smoker	xx (xx.x)	xx (xx.x)	xx (xx.x)
Race	White	xx (xx.x)	xx (xx.x)	xx (xx.x)
	Black	xx (xx.x)	xx (xx.x)	xx (xx.x)
	Mixed race	xx (xx.x)	xx (xx.x)	xx (xx.x)
	Asian - Indian	xx (xx.x)	xx (xx.x)	xx (xx.x)
	Asian - Bangladeshi	xx (xx.x)	xx (xx.x)	xx (xx.x)
	Asian - Pakistani	xx (xx.x)	xx (xx.x)	xx (xx.x)
	Asian - other	xx (xx.x)	xx (xx.x)	xx (xx.x)
	Other	xx (xx.x)	xx (xx.x)	xx (xx.x)
Blood Type	Unknown	xx (xx.x)	xx (xx.x)	xx (xx.x)

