None of the above		xx (xx.x)	xx (xx.x)	xx (xx.x)	xx (xx.x)

*Non-exclusive categories

Table 8.2.8 Prophylaxis use

Characteristic*	Infected at baseline N = xxx	Infected at follow-up N = xxx	Not infected N = xxx	Total N = xxx
Azithromycin	xx (xx.x)	xx (xx.x)	xx (xx.x)	xxx (xx.x)
Chloroquine	xx (xx.x)	xx (xx.x)	xx (xx.x)	xxx (xx.x)
Hydroxychloroquine	xx (xx.x)	xx (xx.x)	xx (xx.x)	xxx (xx.x)
Ivermectin	xx (xx.x)	xx (xx.x)	xx (xx.x)	xxx (xx.x)
Lopinavir/Ritonavir	xx (xx.x)	xx (xx.x)	xx (xx.x)	xxx (xx.x)
Other (will be specified further based on the data)	xx (xx.x)	xx (xx.x)	xx (xx.x)	xxx (xx.x)
Unknown	xx (xx.x)	xx (xx.x)	xx (xx.x)	xxx (xx.x)

*Non-exclusive categories

Table 8.2.9 PPE usage at baseline

Characteristic	Infected at baseline N = xxx	Infected at follow-up N = xxx	Not infected N = xxx	Total N = xxx
Mask				
Yes - always	xx (xx.x)	xx (xx.x)	xx (xx.x)	xxx (xx.x)
Yes – not always	xx (xx.x)	xx (xx.x)	xx (xx.x)	xxx (xx.x)
No	xx (xx.x)	xx (xx.x)	xx (xx.x)	xxx (xx.x)
Gown				
Yes - always	xx (xx.x)	xx (xx.x)	xx (xx.x)	xxx (xx.x)
Yes – not always	xx (xx.x)	xx (xx.x)	xx (xx.x)	xxx (xx.x)
No	xx (xx.x)	xx (xx.x)	xx (xx.x)	xxx (xx.x)
Eye protection				
Yes - always	xx (xx.x)	xx (xx.x)	xx (xx.x)	xxx (xx.x)
Yes – not always	xx (xx.x)	xx (xx.x)	xx (xx.x)	xxx (xx.x)
No	xx (xx.x)	xx (xx.x)	xx (xx.x)	xxx (xx.x)
Gloves				
Yes - always	xx (xx.x)	xx (xx.x)	xx (xx.x)	xxx (xx.x)
Yes – not always	xx (xx.x)	xx (xx.x)	xx (xx.x)	xxx (xx.x)
No	xx (xx.x)	xx (xx.x)	xx (xx.x)	xxx (xx.x)
PPE Yes - always used				
At least one type	xx (xx.x)	xx (xx.x)	xx (xx.x)	xxx (xx.x)
At least two types	xx (xx.x)	xx (xx.x)	xx (xx.x)	xxx (xx.x)
At least three types	xx (xx.x)	xx (xx.x)	xx (xx.x)	xxx (xx.x)
All four types	xx (xx.x)	xx (xx.x)	xx (xx.x)	xxx (xx.x)

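### SAP 6.3.7 and 6.3.8 count follow-up cases' prophylaxis and PPE in weeks after infection, and the pre-infection window is only an undecided addition that the shells do not show

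*SAP*

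**What the plan says.** SAP 6.3.7 (prophylaxis) sets a different rule for each infection group:

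- Infected at entry: "For HCWs with COVID-19 at entry: prophylaxis treatments used before the COVID-19 infection date will be described".
- Infected during follow-up: "For HCWs with COVID-19 at follow-up: prophylaxis treatments used over the entire follow-up time available in the data cut". It then adds: "In addition, prophylaxis treatments used within 2 or 4 weeks (TBD) before COVID-19 infection date will be described".
- Never infected: "For HCWs with no COVID-19 infection at any time: prophylaxis treatments used over the entire follow-up time available in the data cut", with an additional window of 2 or 4 weeks, also undecided, counted back from the data cut.

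SAP 6.3.8 (PPE) follows the same pattern for follow-up cases: "For HCWs with COVID-19 at follow-up: overall PPE usage over the entire follow-up time available in the data cut". Its entry cases are handled differently: "For HCWs with COVID-19 at entry: responses to the baseline survey will be used".

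Both sections plan stacked bar charts over follow-up, drawn separately for infected and uninfected HCWs and offered as a means of comparing them. Neither says that the infected series stops at infection. The shell for 6.3.7 is Table 8.2.8, with one column per infection group and one row per drug. The shell for 6.3.8 is titled "Table 8.2.9 PPE usage at baseline". The shell that sets infection against prophylaxis (yes/no) and PPE (yes/no) is "Table 8.2.2 Primary and Secondary Outcomes at baseline and follow-up among the overall population"; it states no time window for either.

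**The concern.** These displays compare exposure between infected and uninfected HCWs. Exposure that begins after the event cannot have influenced it. Counting it in one group only makes the groups differ even when prophylaxis does nothing. Within Table 8.2.8, two adjacent columns of infected HCWs are also built on different rules.

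Protocol 8.7.1 leaves it to the SAP to define which treatment exposure can be attributed to an outcome, and SAP 7.6 recognises protopathic bias. The remedies in 7.6 (the subgroups with a negative PCR at index date or with serology) do not remove drugs first reported after an infection that occurs during follow-up.

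At stake is how the descriptive evidence on the primary question is read, and on PPE, which is among the factors named in the secondary objectives.

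**Working it through.** **1. The main windows side by side**

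| Group | Prophylaxis (6.3.7) | PPE (6.3.8) |
|---|---|---|
| Infected at entry | before infection only | baseline survey response |
| Infected in follow-up | entire follow-up | entire follow-up |
| Never infected | entire follow-up | entire follow-up |

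Only the prophylaxis column has a cut at infection, and only for entry cases.

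**2. Does the window reach past infection?** Yes. Under SAP 3.1, weekly surveys run for 12 weeks from enrolment and end early only on death or loss to follow-up. If infection fell evenly over weeks 1 to 12 (assumption), the mean number of surveys after infection would be (11 + 10 + … + 0)/12 = 66/12 = 5.5 of 12.

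**3. Can a drug first reported after infection be counted?** Yes. SAP 3.5.2 and 3.6.5 count a listed drug reported under either prophylactic or concomitant medication, with no condition on its date.

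**4. Size for drugs.** The plan gives no figure to reproduce. Let p be the share using a listed drug before infection, equal in infected and uninfected HCWs (no effect). Let q be the share of infected non-users who report a listed drug only afterwards (assumed). Then ever-use in cases is a = p + (1 − p)q, and the apparent odds ratio is [a/(1 − a)] / [p/(1 − p)]. The protocol's enrolment target suggests p = 0.75 and the sample-size section p = 0.80; the other values show the range.

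| p | q = 0.10 | q = 0.25 | q = 0.50 |
|---|---|---|---|
| 0.20 | 1.56 | 2.67 | 6.00 |
| 0.50 | 1.22 | 1.67 | 3.00 |
| 0.75 | 1.15 | 1.44 | 2.33 |
| 0.80 | 1.14 | 1.42 | 2.25 |

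Example: p = 0.75, q = 0.25 gives a = 0.8125, and (0.8125/0.1875)/(0.75/0.25) = 4.33/3 = 1.44. The true value is 1.00 throughout.

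**5. PPE.** Under the collapse table in 6.3.8, one lesser answer turns an always-user into a not-always user, so extra surveys can only move people out of the always category. If 60% of both groups are always-users and 25% or 50% of the infected ones give one lesser answer after infection (all assumed), the odds ratio for not-always use is (0.55/0.45)/(0.40/0.60) = 1.83 or (0.70/0.30)/(0.40/0.60) = 3.50.

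**6. The additional window.** For never-infected HCWs it ends at the data cut. Surveys stop 12 weeks after enrolment, so a window of L weeks holds no survey for anyone enrolled more than 12 + L weeks before the cut: 14 weeks for L = 2, 16 weeks for L = 4.

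**7. Would cutting only the cases do?** No. Take no effect, 75% users at entry, infection even over weeks 1 to 12, and a weekly start rate h among non-users (all assumed). Non-use is 0.25(1 − h)^12 in never-infected HCWs. In cases it is 0.25 times the mean of (1 − h)^(w − 1) over infection weeks w = 1 to 12. For h = 2%, 5% and 10% the ever-use odds ratio is 0.84, 0.66 and 0.43, so prophylaxis looks protective.

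**The case against.** The strongest reply is that these are descriptive tables, that a pre-infection window is already planned in both sections, and that the SAP nowhere calls the whole-follow-up summary pre-infection exposure. All of that is true. It does not answer that the main summary is the contaminated one, or that the pre-infection window has neither a length nor a place in the shells.

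A reader might go further than the documents allow in five ways:

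- *That drugs taken to treat COVID-19 will automatically count as prophylaxis.* The concomitant section is headed as being for purposes other than COVID-19, so such a drug properly belongs in neither section. Protocol Appendix 2 offers no separate field for it, however, and no date condition would catch it if reported. Miscounting is possible, not certain.
- *That entry cases are cut at infection for PPE too.* They are not; the baseline response is used. The inconsistency between the two infected groups on cutting at infection concerns prophylaxis only.
- *That time off work will be recorded as not using PPE.* The weekly item asks about PPE at confirmed exposures in the past week, and the documents do not say how a week without exposure is recorded. The PPE arm is the weaker one.
- *That Table 8.2.2 will show a distorted relative risk.* Its timing is unstated, which is a gap and not a wrong rule. If it were filled by ever-use, with 2,000 unexposed, 8,000 exposed and 10% infected in each, moving 20, 40 or 60 of the 200 infected non-users would give relative risks of 1.12, 1.28 or 1.48; for 20, (820/8,020)/(180/1,980) = 1.12. That use of the table is an assumption.
- *That the primary estimate is biased.* The crude and adjusted hazard ratios come from the time-to-infection model in 6.4.1, and these summary windows do not define its risk set.

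**Conclusion.** The point holds for the descriptive analyses. As written, the main prophylaxis and PPE summaries for follow-up cases include weeks after infection, and for prophylaxis this contradicts the rule for entry cases. The drug comparison can be biased against prophylaxis. At the plan's own exposure levels (75% to 80%) the apparent odds ratio under no effect runs from about 1.1 to 2.3 as the assumed share of late reporters goes from 10% to 50%. The documents give no basis for choosing within that range, nor any firm size for PPE. The planned extra window does not cure this, because it is secondary, undecided and absent from the shells, and its comparator can fall after an HCW's surveys have ended. The primary Cox model is not directly affected. It should be corrected before the tables are produced.

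**What to change.** - In SAP 6.3.7 and 6.3.8, make the pre-infection window the main summary for follow-up cases and set one length. Do the same in 6.3.3, 6.3.4 and 6.3.6, which use the same pattern. In 6.3.4, days and hours worked are summed, so unequal windows distort them directly.
- Give never-infected HCWs a window of the same length that ends at a survey they completed, such as a matched follow-up week or their last survey, and not at the data cut.
- Do not cut cases at infection while leaving never-infected HCWs at full follow-up (step 7 of the working).
- Stop the infected HCWs' series in the stacked bar charts at the infection date.
- Show the window in the shells, and state in Table 8.2.2 that prophylaxis and PPE are classified by it.
- Put drugs first started on or after infection in a separate row.
- Retitle Table 8.2.9, whose reference to baseline does not match the follow-up rule in 6.3.8.

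The cost is SAP wording, shell edits and a date filter on data already collected. The shorter window uses fewer survey weeks per HCW. The whole-follow-up summary can stay as a secondary display, labelled as including time after infection.
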